5.1 DOSE MODIFICATIONS

Subjects will be monitored continuously for adverse events (AEs) while on study therapy. Subjects will be instructed to notify their physician immediately for any and all AEs. Adverse events will be graded according to CTCAE version 4.0. Dose modifications will be made for:

- a) Subjects who experience an adverse event of grade 3 or greater that is probably related to the study drug will be withdrawn from study and will be followed until the resolution of toxicity.
- b) Subjects who experience an adverse event of grade 3 or greater that is possibly related to the study drug will not be retreated with subsequent cycles until the adverse event resolves to grade 1 or less. Subjects who require greater than 14 days of treatment delay due to toxicity that is possibly related to the study drug will be removed from the study and followed until resolution of toxicity.

5.2 DISCONTINUATION OF THERAPY

Study therapy MUST immediately be discontinued for any the following reasons:

- Radiographic evidence of tumor progression as defined by the Immune Related Response Criteria (see section 7.5)
- Withdrawal of informed consent (subject's decision to withdraw for any reason)
- Any clinical adverse event, laboratory abnormality, inter-current illness, or progression of disease which, in the opinion of the Principal Investigator, indicates that continued participation in the study is not in the best interest of the subject
- Pregnancy
- Termination of the study by the sponsor
- Imprisonment or the compulsory detention for treatment of either a psychiatric or physical (e.g., infectious disease) illness
- Subjects will also be discontinued based on 5.1a.

5.3 EMERGENCY UNBLINDING

Subjects and Investigators will be unblinded as to treatment allocation after **all patients** have completed the study and the **database is locked** (routine unblinding). In the event of an emergency that would require the investigator to be aware of the treatment allocation prior to the end of the trial, the investigator can obtain this information, on a per Patient basis, from the Sponsor's electronic database at the Investigative site. The investigator is not required to contact the sponsor or sponsors representative prior to unblinding, but is encouraged to do so if there are any questions regarding the unblinding procedure or need to unblind.

Examples of events that would qualify as emergent are as follows:

- A grade 3 or greater AE which are "probably or definitely" related to study drug administration, such as a grade 3 infusion reaction, **and** where treatment assignment information is essential for the management of the event. Per section 5.1 (a), this type of reaction would require that the patient receives no further doses, and is followed until the resolution of the toxicity.
- Any suspected, unexpected, serious adverse reaction (SUSAR)
- Pregnancy

5.4 STUDY PROCEDURES

Screening-14 days are allowed to complete all procedures and the first dose (C1D1) must occur within 7 days of randomization:

[figure not shown]
- Informed Consent
- Medical History
- Physical Exam
- Height
- Weight
- Vital Signs
- ECOG Evaluation
- Hematology panel: CBC with differential and platelets
- Chemistry panel
- PT/aPTT/INR
- Urinalysis
- Serum Pregnancy
- C-Reactive Protein
- EORTC QLQ-C30
- Prior Medications
- TNM staging
- Randomization- after confirmation that subject meets all inclusion/exclusion criteria
- DEXA Scan- Lean Body Mass/Body Composition
- Tumor Measurements- Assessments can include CT or MRI, and whichever modality is chosen for the initial tumor assessment must be used for the week 8 assessment. The choice of modality should be based primarily on the type of scan that the patient has previously received as their standard of care. Standard of care scans obtained within 28 days prior to C1D1 may be used as screening scans.

DEXA scans should be scheduled to occur prior to CT or MRI tumor measurements. In the event that these scans are obtained prior to the DEXA scan (such as scans done for standard of care), then there must be a 10 day washout prior to obtaining the DEXA scan.

PT023: Screening and Randomization

[figure not shown]
Options pertaining to CT Availability

A. CT Available Before Screening (within 28 days of dosing)

*CT with Contrast (standard of care) performed within 28 days prior to treatment on study may be used as the Baseline Scan.
 **DEXA should be completed no earlier than 10 days after CT with Contrast (standard care).

B. CT Unavailable Before Screening

*DEXA may be completed anytime during Screening before Randomization.
 **Protocol-required CT may be completed anytime after Randomization but before the first dose of study drug.

Note: These schema show the maximum window sizes for completion of the radiologic procedures. The key elements are:

- *Baseline tumor assessment should be done within 28 days of C1 D1*
- *A 10 day washout period is required for DEXA scans acquired after a CT*
- *Alternatively, the DEXA scan can be obtained prior to tumor measurements*

Cycle 1 Day 1 (C1D1):

- Physical Exam
- Weight
- Vital Signs (pre-infusion)
- ECOG Evaluation
- Hematology panel: CBC with differential, platelets (pre-infusion)
- Chemistry panel (pre-infusion)

*Urinalysis, Hematology and Chemistry panels that are obtained for the purpose of screening a subject, and that are drawn within 72 hours of C1D1, may also be used for the C1D1 baseline safety lab values.

- Urinalysis (pre-infusion)
- CRP (pre-infusion)
- PK Sampling (pre-infusion)
- Study Drug infusion
- Vital signs (60 minutes post-infusion)
- PK Sampling (30-90 minutes post-infusion)
- Adverse Event monitoring
- Concomitant Medications

Cycle 2 Day 1 +/- 2 days (C2D1):

- Physical Exam
- Weight
- Vital Signs (pre-infusion)
- ECOG Evaluation
- Hematology panel: CBC with differential, platelets (pre-infusion)
- Chemistry panel and serum pregnancy (pre-infusion same tube)
- Urinalysis (pre-infusion)
- CRP (pre-infusion)
- PK Sampling (pre-infusion)
- Study Drug infusion
- Vital signs (60 minutes post-infusion)
- PK Sampling (30-90 minutes post-infusion)
- Adverse Event monitoring
- Concomitant Medications

Cycle 3 Day 1 +/- 2 days (C3D1):

- Physical Exam
- Weight
- Vital Signs (pre-infusion)
- ECOG Evaluation
- Hematology panel: CBC with differential, platelets (pre-infusion)
- Chemistry panel (pre-infusion)
- Urinalysis (pre-infusion)
- CRP (pre-infusion)
- PK Sampling (pre-infusion)

- Study Drug infusion
- Vital signs (60 minutes post-infusion)
- PK Sampling (30-90 minutes post-infusion)
- Adverse Event monitoring
- Concomitant Medications

Cycle 4 Day 1 +/- 2 days (C4D1):

- Physical Exam
- Weight
- Vital Signs (pre-infusion)
- ECOG Evaluation
- Hematology panel: CBC with differential, platelets (pre-infusion)
- Chemistry panel and serum pregnancy (pre-infusion same tube)
- Urinalysis (pre-infusion)
- CRP (pre-infusion)
- PK Sampling (pre-infusion)
- Study Drug infusion
- Vital signs (60 minutes post-infusion)
- PK Sampling (30-90 minutes post-infusion)
- Adverse Event monitoring
- Concomitant Medications

Cycle 5 Day 1 +/- 2 days (C5D1):

- Physical Exam
- Weight
- Vital Signs (pre-infusion)
- ECOG Evaluation
- Hematology panel: CBC with differential, platelets (pre-infusion)
- Chemistry panel (pre-infusion)
- Urinalysis (pre-infusion)
- CRP (pre-infusion)
- PK Sampling (pre-infusion)
- Study Drug infusion
- Vital signs (60 minutes post-infusion)
- PK Sampling (30-90 minutes post-infusion)
- Adverse Event monitoring
- Concomitant Medications
- EORTC QLQ-C30
- DEXA scan for lean body mass/body composition (+/- 3 days of C5D1)
- Tumor Measurements (+/- 3 days of C5D1- **AFTER DEXA SCAN**)

Cycle 6+/- Follow up visits will occur every 14 days (+/- 2 days) for all subjects who remain on trial:

- Physical Exam
- Weight

- Vital Signs (pre-infusion)
- ECOG Evaluation
- Hematology panel: CBC with differential, platelets (pre-infusion)
- Chemistry panel and serum pregnancy (pre-infusion same tube). Serum pregnancy to be completed every 2 cycles.
- Urinalysis (pre-infusion)
- CRP (pre-infusion)
- PK Sampling (pre-infusion)
- Study Drug infusion
- Vital signs (60 minutes post-infusion)
- PK Sampling (30-90 minutes post-infusion)
- Adverse Event monitoring
- Concomitant Medications
- Tumor Measurements (every 8 weeks, i.e. within 7 days prior to C9D1, C13D1 etc.). Upon documentation of radiographic progression, confirmatory tumor measurements to be repeated at 4 weeks +/- 3 days only for patients who elect to continue on therapy until confirmation of progression. If this scan confirms progression, treatment is to be discontinued. If the confirmatory measurements indicate stable disease or better, the patient may elect to continue treatment with radiographic tumor assessments every 8 weeks from Day 1 of the current treatment cycle until progression.

End of Study Visit- This visit should be completed within 14 days for any subject who elects to come off trial or who comes off due to AEs, toxicities, or decline in performance status:

- Physical Exam
- Weight
- Vital Signs
- ECOG Evaluation
- Hematology panel: CBC with differential, platelets
- Chemistry panel
- Urinalysis
- CRP
- Adverse Event monitoring
- Serum Pregnancy
- PK Sampling
- EORTC QLQ-C30
- Concomitant Medications / Non-Drug Therapies review
- DEXA Scan--for any subject who completes visits at least through C3D1, but discontinues prior to C5D1
- Tumor Measurements--for subjects with clinical progression, every effort should be made to obtain radiographic restaging. If subjects are discontinued due to evidence of progressive disease, then tumor measurements do not need to be repeated.

Follow up for Overall Survival

Subjects, who come off trial for any reason after C1D1, will be contacted by phone after 30 days of the last dosing visit for adverse events and ECOG performance status, and at every 4-6 weeks

there after to assess ECOG performance status. Patients will be considered lost to follow up after 3 documented consecutive unsuccessful contact attempts. Prior to any interim analysis, and once the trial has been completed, any subjects who have been lost to follow up will be queried against the Social Security Administration's Death Master File to determine date of death.

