^j Following Cycle 6 Day 1, tumor measurements are to be repeated every 8 weeks (within 7 days prior to C9D1, C13D1, C17D1, etc.). Upon documented progression, confirmatory tumor measurements are to be repeated at 4 weeks +/- 3 days, for patients who elect to continue therapy until confirmation of progression.

^k Tumor measurements should be performed, if possible, for subjects with clinical progression, to obtain radiographic restaging.

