The same method of assessment and the same technique should be used to characterize each identified and reported lesion at baseline and during follow-up. Imaging-based evaluation is preferred to evaluation by clinical examination when both methods have been used to assess the antitumor effect of a treatment.

Clinical lesions. Clinical lesions will only be considered measurable when they are superficial (e.g., skin nodules and palpable lymph nodes). In the case of skin lesions, documentation by color photography, including a ruler to estimate the size of the lesion, is recommended.

Helical (or Spiral) CT and MRI. These techniques should be performed with cuts of 5 mm or less in slice thickness contiguously. Spiral CT should be performed using a ≤ 5 mm contiguous reconstruction algorithm. This applies to tumors of the chest, abdomen, and pelvis. Head and neck tumors and those of extremities usually require specific protocols.

7.5.1 Immune Related Response Criteria:

Evaluation of Target Lesions

Evaluation of radiographic response will be conducted using the Immune Related Response Criteria (irRC), as described by Wolchok, et al⁶⁰. “For irRC, only index and measurable new lesions are taken into account. At the baseline tumor assessment, the sum of the products of the two largest perpendicular diameters (SPD) of all index lesions (five lesions per organ, up to 10 visceral lesions and five cutaneous index lesions) is calculated. At each subsequent tumor assessment, the SPD of the index lesions and of new, measurable lesions ($\geq 10 \times 10$ mm; up to 5 new lesions per organ: 5 new cutaneous lesions and 10 visceral lesions) are added together to provide the total tumor burden:”

$$\text{Tumor Burden} = \text{SPD}_{\text{index lesions}} + \text{SPD}_{\text{new, measurable lesions}}$$

Complete Response (irCR): irCR, complete disappearance of all lesions (whether measurable or not, and no new lesions). Confirmation by a repeat, consecutive assessment no less than 4 weeks from the date first documented.

Partial Response (irPR): irPR, decrease in tumor burden $\geq 50\%$ relative to baseline confirmed by a consecutive assessment at least 4 weeks after first documentation.

Progressive Disease (irPD): irPD, increase in tumor burden $\geq 25\%$ relative to nadir (minimum recorded tumor burden) confirmation by a repeat, consecutive assessment no less than 4 weeks from the date first documented.

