- If a patient is classified as having irPD at a post-baseline tumor assessment, then confirmation of irPD by a second scan in the absence of rapid clinical deterioration is required. The definition of confirmation of progression represents an increase in tumor burden $\geq 25\%$ compared with the nadir at two consecutive time points at least 4 weeks apart. **It is recommended that this be done at the discretion of the investigator because follow-up with observation alone may not be appropriate for patients with a rapid decline in performance status.**

Stable Disease (irSD): irSD, not meeting criteria for irCR or irPR, in absence of irPD.

Table 1. Comparison between WHO criteria and the irRC

	WHO	irRC
New, measurable lesions (i.e., $\geq 5 \times 5$ mm)	Always represent PD	Incorporated into tumor burden
New, nonmeasurable lesions (i.e., $< 5 \times 5$ mm)	Always represent PD	Do not define progression (but preclude irCR)
Non-index lesions	Changes contribute to defining BOR of CR, PR, SD, and PD	Contribute to defining irCR (complete disappearance required)
CR	Disappearance of all lesions in two consecutive observations not less than 4 wk apart	Disappearance of all lesions in two consecutive observations not less than 4 wk apart
PR	$\geq 50\%$ decrease in SPD of all index lesions compared with baseline in two observations at least 4 wk apart, in absence of new lesions or unequivocal progression of non-index lesions	$\geq 50\%$ decrease in tumor burden compared with baseline in two observations at least 4 wk apart
SD	50% decrease in SPD compared with baseline cannot be established nor 25% increase compared with nadir, in absence of new lesions or unequivocal progression of non-index lesions	50% decrease in tumor burden compared with baseline cannot be established nor 25% increase compared with nadir
PD	At least 25% increase in SPD compared with nadir and/or unequivocal progression of non-index lesions and/or appearance of new lesions (at any single time point)	At least 25% increase in tumor burden compared with nadir (at any single time point) in two consecutive observations at least 4 wk apart

Table 2. Derivation of irRC overall responses

Measurable response Index and new, measurable lesions (tumor burden),* %	Nonmeasurable response		Overall response Using irRC
	Non-index lesions	New, nonmeasurable lesions	
↓100	Absent	Absent	irCR [†]
↓100	Stable	Any	irPR [†]
↓100	Unequivocal progression	Any	irPR [†]
↓ ≥ 50	Absent/Stable	Any	irPR [†]

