Immune Related Response Criteria: Tumor response will be assessed by using immune-related response criteria (irRC). The imaging service provider (core laboratory) will acquire images from clinical sites. Review of image data will be conducted in the core lab by qualified and trained radiologists blinded to treatment status. The procedures used for CT/MRI image analysis, reporting of tumor response data and storage and archiving of images will follow the standards laid out in the prospectively determined Imaging Review Charter.

irRC Evaluation:

The detailed evaluation methodology is documented in the Imaging Review Charter. Briefly, for each imaging session, the sum of the products of the two largest perpendicular diameters (SPD) of all index lesions (5 lesions per organ, up to 10 visceral and 5 cutaneous lesions with

a minimum size of $\geq 5 \times 5$ mm) will be calculated. Index lesions will be identified at baseline, and will be followed throughout the patient's participation in this study. At each subsequent imaging assessment, new lesions (defined as a lesion with $> 5 \times 5$ mm measurements) will have their products of diameters measured for use in calculating tumor burden. Tumor burden will be calculated by summing the SPD of target lesions with the SPD of the new measurable lesions.

Table 1: irRC Response Definitions:

Complete Response (irCR):	Disappearance of all lesions in two consecutive observations not less than 4 weeks apart
Partial Response (irPR):	$\geq 50\%$ decrease in tumor burden compared with baseline in two observations at least 4 weeks apart
Stable Disease (irSD):	50% decrease in tumor burden compared with baseline cannot be established nor 25% increase compared with nadir
Progressive Disease (irPD):	At least 25% increase in tumor burden compared with nadir (at any single time point) in two consecutive observations at least 4 weeks apart
Not Evaluable (NE)	Progression has not been documented and one or more index lesions have not been assessed or have been assessed using a different method than baseline that makes comparability impossible.

Table 2: Derivation of irRC Overall Response

Overall lesions response at each assessment			
Index and new lesions (tumor burden), * %	Non-Target Lesions	New Lesions	Overall Response
$\downarrow 100$	Absent	Absent	irCR †
$\downarrow 100$	Stable	Any	irPR †
$\downarrow 100$	Unequivocal progression	Any	irPR †
$\downarrow > 50$	Absent/Stable	Any	irPR †

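### The confirmatory-scan window of 4 weeks ± 3 days opens before the 4-week minimum for confirming irPD, so an on-schedule scan on days 25–27 cannot confirm progression as written

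*Protocol*

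**What the plan says.** **Schedule.** Protocol 5.4 (Study Procedures, Cycle 6+) provides, once radiographic progression is documented, for "confirmatory tumor measurements to be repeated at 4 weeks +/- 3 days only for patients who elect to continue on therapy". Footnote j of the Study Calendar repeats the timing: "Upon documented progression, confirmatory tumor measurements are to be repeated at 4 weeks +/- 3 days".

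**Confirmation rule.** The irPD definition in protocol 7.5.1 reads, in part, "minimum recorded tumor burden) confirmation by a repeat, consecutive assessment no less than 4 weeks from the date first documented". The bullet beneath it describes confirmation as an increase of at least 25% "compared with the nadir at two consecutive time points at least 4 weeks apart". Table 1 of that section gives the same minimum. SAP 3.2, Table 1, defines irPD as "At least 25% increase in tumor burden compared with nadir (at any single time point) in two consecutive observations at least 4 weeks apart", and the footnote to SAP Table 2 repeats the 4-week minimum.

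**What depends on the result.** After the confirmatory scan, protocol 5.4 describes two outcomes. If progression is confirmed, treatment stops. If the scan shows stable disease or better, the patient may continue, with 8-weekly scans counted from Day 1 of the current cycle. Protocol 5.2 makes irRC progression a mandatory reason to stop. Protocol 7.5 says the central imaging vendor tells sites only whether the result is progression or stable disease. For progression, the PFS definition in SAP 3.2 refers to Table 1, which contains the confirmed-irPD rule.

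**The concern.** The window and the rule use the same 4 weeks, but the window allows 3 days on the early side and the rule is a strict minimum. No text in either document extends the 3-day tolerance to the rule. A site can therefore follow the schedule exactly and produce a scan that the definition does not accept.

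The difficult case is a scan on day 25, 26 or 27 with tumor burden still at least 25% above nadir. It is not confirmed irPD because the interval is too short. It is not clearly stable either. Protocol 7.5.1 defines irSD by the absence of irPD, and neither document says whether an irPD confirmed too early counts as absent. The central reader must report one result or the other without a written rule.

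At stake are the irPD classification, PFS status or date, DCR and the trigger for stopping therapy. Two scans showing growth could end in a censored PFS time: SAP Table 3 censors a patient who stops treatment for toxicity or another reason at the last adequate assessment.

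**Working it through.** **Inputs**
- Window: 4 weeks ± 3 days from documented progression (protocol 5.4, visit text and footnote j).
- Minimum: 4 weeks = 28 days (protocol 7.5.1; SAP 3.2, Tables 1 and 2).
- Ordinary scans: every 8 weeks, within 7 days before C9D1, C13D1 and so on (protocol 5.4).
- Cycle length: 14 days (protocol 5.4).

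**Step 1. Window against minimum.** The window is 28 − 3 to 28 + 3, i.e. days 25, 26, 27, 28, 29, 30 and 31: seven days. Days below 28 are 25, 26 and 27. That is 3/7 = 43% of the permitted days; 4 of 7 satisfy both texts.

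**Step 2. Does the answer depend on the starting point?** The window runs from documentation of progression. Reading is central, so documentation may follow the index scan by a lag of L days. A scan on window day d is then d + L days after the index scan, and the scan-to-scan rule needs d + L ≥ 28.

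| Lag L (days) | Window days too early, scan to scan |
|---|---|
| 0 | 25, 26, 27 |
| 1 | 25, 26 |
| 2 | 25 |
| 3 or more | none |

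With a lag of 3 days or more, the conflict disappears against the rules that count between two assessments: the 7.5.1 bullet and SAP Tables 1 and 2. It does not disappear against the irPD definition in 7.5.1, which counts from the date progression was first documented. That is the event that opens the window, so d ≥ 28 is needed whatever the lag, and days 25–27 still fail.

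**Step 3. How far could confirmation slip?** Suppose the first irPD is found at a scheduled 8-weekly scan and the repeat on day 26 is not accepted.
- *Ordinary calendar.* The next scheduled scan is nominally 56 days after the first irPD scan. Against the 28-day minimum the slip is 56 − 28 = 28 days, about 4 weeks. Two successive scans, each taken in its 7-day window, are 56 ± 7 = 49 to 63 days apart, so the slip is 21 to 35 days.
- *Handled as stable.* The next scan is 8 weeks from Day 1 of the current cycle. With 14-day cycles, Day 1 lies 0 to 14 days before the repeat scan. The next scan is therefore 56 − 14 = 42 to 56 days after it, i.e. up to about 8 weeks.

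**Step 4. Which endpoints are exposed?**
- OS: none; it does not use irPD.
- PFS: status or date can change. SAP Table 3 still counts an investigator's claim of clinical progression, and most deaths, as events.
- DCR: mainly when irPD appears at the first post-baseline scan. With an earlier irSD, best overall response already gives disease control.

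**The case against.** The strongest reply is that a visit window is a practical tolerance and that the plan has other ways to handle these patients. Protocol 7.5.1 waives the second scan in rapid clinical deterioration and leaves confirmation to the investigator's discretion. Protocol 5.2 lets the investigator stop therapy when continuing is not in the patient's interest. The central vendor reports one of two results, which correspond to the two outcomes in 5.4. SAP 3.2 leaves detailed irRC method to the Imaging Review Charter, which is not part of these documents and could contain a tolerance.

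Much of this stands as a limit on the consequences. A reader might infer that these patients have no stopping rule; that goes too far, because the routes above exist. But the discretion concerns patients for whom waiting is unsuitable and does not shorten the interval for those who do wait. The two-result report gives no basis for choosing between the results. A tolerance in the charter would still leave the protocol and SAP stating a strict minimum.

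Other stronger readings are also unsupported:
- *About 4 in 10 confirmatory scans are invalid.* The 43% is a share of permitted days. It would be a share of scans only if scans were spread evenly over the window, and the documents give no distribution.
- *Each early scan costs 8 weeks.* That interval belongs only to the branch for stable disease or better.
- *PFS is systematically dated late.* Neither document says whether confirmed irPD is dated to the first or the second scan. If to the first, later confirmation alone moves no date.
- *The treatment comparison is biased.* Nothing in the documents points to a difference between arms, and the trial is double blind.

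**Conclusion.** The contradiction holds. As written, an on-schedule scan on day 25, 26 or 27 cannot confirm irPD, and a scan on those days that still meets the growth threshold has no clear classification. The finding assumes only that 4 weeks means 28 days and that the stated minimums are literal. If the window runs from a read date at least 3 days after the index scan, the conflict is confined to the irPD definition in protocol 7.5.1, but it does not vanish.

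The reach is limited to patients who continue therapy after a first irPD. The effect is on secondary endpoints and on the trigger for stopping treatment, through possible misclassification or misdating. The number of patients affected cannot be estimated from the documents.

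**What to change.** Reconcile the visit text in protocol 5.4 and calendar footnote j with protocol 7.5.1 and SAP 3.2, Tables 1 and 2. Every scan day that the schedule permits should be able to satisfy the confirmation rule used in the analysis. Then align the continue/stop sentences in 5.4 with the result. Because this scan governs stopping treatment, whether the schedule or the definition changes is for the sponsor to decide.

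While editing, state whether documentation means the scan date or the central-read date, and which scan dates a confirmed irPD for PFS. The cost is a few words in the protocol, the SAP or both, with no extra procedure.
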